6.1.1.2 Uroflowmetry

The maximum flow rate (free Q_{max}), average flow rate (free Q_{ave}), voided volume, and voiding time will be evaluated based on uroflowmetry.

DeltaQ is defined as follows³⁾:

$$\text{DeltaQ} = \text{free } Q_{max} - \text{free } Q_{ave}$$

6.1.1.3 Evaluation of Symptom Scores

The endpoints to be used for the evaluation of symptom scores are IPSS, QOL score, and OABSS.

6.1.1.3.1 IPSS and QOL Score

Voiding symptoms and storage symptoms will be evaluated using the IPSS and QOL score.

The IPSS total score will be the total score of questions 1 to 7, and a score of 0 to 7 points will be classified as mild, a score of 8 to 19 points will be classified as moderate, and a score of 20 to 35 points will be classified as severe. The total of the scores for question 1 on post-micturition symptoms and questions 3, 5, and 6 on voiding symptoms will be taken to be the IPSS voiding symptoms score, and the total of the scores for questions 2, 4, and 7 on storage symptoms will be taken to be the score for IPSS storage symptoms.

The score for the question "If you were to spend the rest of your life with your urinary condition as it is right now, how would you feel about that?" will be taken to be the IPSS QOL score, and a score of 0 to 1 points will be classified as mild, a score of 2 to 4 points will be classified as moderate, and a score of 5 to 6 points will be classified as severe.

6.1.1.3.2 Overactive Bladder Symptoms Score (OABSS)

The OAB symptoms will be evaluated using OABSS.

The total OABSS score is defined as the total score of all questions. A score of 5 points or less is considered mild, a score of 6 to 11 points is considered moderate, and a score of 12 points or more is considered severe.

6.1.1.4 King's Health Questionnaire (KHQ)

The QOL in DU patients with OAB will be evaluated using the KHQ. The scoring method for each domain based on the Japanese version of KHQ is shown below.

Table 6-1 Scoring Method for Each Domain Based on the Japanese Version of KHQ

Each domain	Scoring method
General health	$(Q1 \text{ score} - 1) / 4 \times 100$
Incontinence impact	$(Q2 \text{ score} - 1) / 3 \times 100$
Restrictions on job/housework	$(Q3a + 3b - 2) / 6 \times 100$
Limitation of physical activities	$(Q4a + 4b - 2) / 6 \times 100$
Limitation of social activities	If Q5c score is ≥ 1 : $(Q4c + 4d + 5c \text{ score} - 3) / 9 \times 100$ *If Q5c score is 0: $(Q4c + 4d + 5c \text{ score} - 2) / 6 \times 100$
Personal relationships	If $Q5a + 5b \geq 2$: $(Q5a+5b-2)/6\times100$ If $Q5a + 5b = 1$: $(Q5a+5b-1)/3\times100$ If $Q5a + 5b = 0$: Handle the score as a missing value (not applicable)
Emotions	$(Q6a + 6b + 6c \text{ score} - 3) / 9 \times 100$
Sleep/energy	$(Q7a + 7b \text{ score} - 2) / 6 \times 100$
Severity measures	$(Q8a + 8b + 8c + 8d + 8e \text{ score} - 5) / 15 \times 100$

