2.3.2 Secondary Endpoints

2.3.2.1 Efficacy

- (1) PFS parameters (filling phase) [Evaluation time points: week 0, week 12]
 - Volume at first desire to void
 - Maximum bladder volume
 - Bladder compliance
 - Appearance of bladder involuntary contraction
 - Bladder volume up to appearance of bladder involuntary contraction
- (2) PFS parameters (voiding phase) [Evaluation time points: week 0, week 12]
 - Detrusor pressure at start of voiding ($P_{det\ open}$)
 - Maximum detrusor pressure ($P_{det\ max}$)
 - Maximum flow rate (Q_{max})

- Average flow rate (Q_{ave})
- Detrusor pressure at maximum flow ($P_{det}Q_{max}$)
- Duration of bladder contraction
- Voided volume
- Post void residual

(3) Uroflowmetry parameters [Evaluation time points: weeks 0, 4, 8, 12]

- Maximum flow rate (free Q_{max})
- Average flow rate (free Q_{ave})
- Voided volume
- Voiding time

(4) Post void residual measured by ultrasonography [Evaluation time points: at registration in observation period, weeks 0, 4, 8, 12]

(5) BVE [Voided volume / (voided volume + post void residual)] [Evaluation time points: weeks 0, 4, 8, 12]

Calculated from the voided volume measured by uroflowmetry and the post void residual measured by ultrasonography

(6) Change in IPSS score at weeks 4, 8, and 12 of the treatment periods relative to baseline (week 0)

- IPSS total score
- IPSS storage symptoms score
- IPSS voiding symptoms score
- IPSS QOL score

(7) Change in IPSS score at weeks 4, 8, and 12 of the treatment periods relative to baseline (week 0)

(8) Change in KHQ score (by domain) at week 12 of the treatment period relative to baseline (week 0)

(9) Change in bladder diary record data at weeks 4, 8, and 12 of the treatment periods relative to baseline (week 0)

- Average number of micturition per 24 hours
- Average number of urgency urinary incontinence episodes per 24 hours
- Average number of urinary urgency episodes per 24 hours
- Average voided volume per urination
- Average number of nocturnal urinations

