11.4 King's health questionnaire (KHQ)

The QOL in DU patients with OAB will be evaluated using the KHQ. The contents of KHQ are shown in Appendix 3.

The principal investigator or subinvestigator will instruct the patients to write down the applicable scores for each question. While the patients are making evaluations, care should be taken not to bias this evaluation, for example by standing next to the patients or talking to them.

The definition of each domain in the Japanese edition of the KHQ and the method for calculating the score are decided with reference to the Clinical Practice Guideline for Overactive Bladder.²³⁾

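### SAP Table 6-1 picks the KHQ Personal relationships formula by the sum of Q5a and Q5b, so a patient with one not-applicable item can score up to 66.7 points below one-item scaling

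*SAP*

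**What the plan says.** SAP 6.1.1.4, Table 6-1, gives three branches for Personal relationships, each chosen by the value of Q5a + Q5b:

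- sum at least 2: (sum − 2)/6 × 100
- sum equal to 1: (sum − 1)/3 × 100
- sum equal to 0: "Handle the score as a missing value (not applicable)"

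The row above it, Limitation of social activities, meets the same difficulty with a single item. "If Q5c score is 0", the amount subtracted falls from 3 to 2 and the divisor from 9 to 6, so the item leaves the scale altogether.

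On the source of the scoring, Protocol 11.4 says that the domain definitions and "the method for calculating the score are decided with reference to the Clinical Practice Guideline for Overactive Bladder". The documents give no other rule for a patient with exactly one not-applicable item in this domain.

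The score is used for a listed secondary endpoint (Protocol 2.3.2.1): "Change in KHQ score (by domain) at week 12 of the treatment period relative to baseline (week 0)". SAP 8.1.8 applies summary statistics, paired t-tests, between-group confidence intervals and Student's t-tests to it, for both change and percentage change. SAP 8.1.11 to 8.1.13 repeat these analyses in subgroups.

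**The concern.** The second branch looks like a rescaling for patients who answered one of the two items: it subtracts 1 and divides by 3, which maps a single answer of 1 to 4 onto 0 to 100. Because the branch is chosen by the sum and not by the count of answered items, most of the patients it seems meant for never reach it. Someone with one item not applicable and the other at 2, 3 or 4 has a sum of at least 2 and is scored as if both items had been answered.

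Three things are at stake for this domain: the level of the score, the size of the change from Week 0 to Week 12, and false change when an item becomes applicable or stops being applicable between the two visits. A baseline of 0 also leaves percentage change undefined, and a one-item responder at level 2 is given a baseline of 0.

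**Working it through.** **Inputs.** The three Personal relationships branches and the Q5c row, all from SAP Table 6-1. The documents give no worked score, so there is no stated figure to reproduce.

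**Step 1: item coding (inferred).** The zero-sum branch and the Q5c row point to 0 as the code for not applicable. Subtracting 2 and dividing by 6 for two items, or subtracting 1 and dividing by 3 for one, fits answers of 1 to 4. The questionnaire form (Protocol Appendix 3) is not readable in the public copy, so this coding is an inference from the table.

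**Step 2: the one-item branch.** It is entered only at sum = 1, where it gives (1 − 1)/3 × 100 = 0. It can return no other value.

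**Step 3: one item not applicable, the other at level x.** The printed rule uses (1 − 1)/3 × 100 for x = 1 and (x − 2)/6 × 100 for x = 2 to 4. One-item scaling uses (x − 1)/3 × 100 throughout.

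| x | Printed rule | One-item scaling | Difference |
|---|---|---|---|
| 1 | 0 | 0 | 0 |
| 2 | 0 | 33.3 | −33.3 |
| 3 | 16.7 | 66.7 | −50.0 |
| 4 | 33.3 | 100 | −66.7 |

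**Step 4: all 25 ordered pairs, each item 0 to 4.** The 16 pairs with both items answered agree under the two rules. The pair (0,0) is missing under both. Of the 8 pairs with exactly one item answered, (0,1) and (1,0) agree at 0. The other six differ: (0,2), (0,3), (0,4) and their reverses.

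**Step 5: change in a patient who has the same single applicable item at both visits.**

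| Fall in x | Printed rule | One-item scaling | Ratio |
|---|---|---|---|
| 2 to 1 | 0 | 33.3 | 0 |
| 3 to 2 | 16.7 | 33.3 | 1/2 |
| 4 to 3 | 16.7 | 33.3 | 1/2 |
| 3 to 1 | 16.7 | 66.7 | 1/4 |
| 4 to 2 | 33.3 | 66.7 | 1/2 |
| 4 to 1 | 33.3 | 100 | 1/3 |

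The score itself is one third or less of its one-item value for x = 2 to 4. Change is at most one half, and a move between 1 and 2 does not register.

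**Step 6: an item becomes applicable.** Suppose that one item is not applicable at Week 0 and at Week 12 is answered at the same level x as the other, which has not moved. The printed rule goes from (0, x) to (x, x): 0 to 0, 0 to 33.3, 16.7 to 66.7 and 33.3 to 100 for x = 1 to 4. The apparent rises are 0, 33.3, 50.0 and 66.7 points. One-item scaling gives no change in these cases.

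**Step 7: scale against the trial.** With 75 patients at 2:1, placebo has 75/3 = 25 and TAC-302 has 50. If every patient contributes a score, one patient at the maximum difference moves the group mean by 66.7/25 = 2.7 points on placebo or 66.7/50 = 1.3 on TAC-302. With fewer contributing patients the shift per patient is larger.

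**The case against.** The strongest objection is that this is an external instrument. Table 6-1 is presented as the scoring for the Japanese version of the KHQ, and the protocol refers to a clinical practice guideline for the method. If that guideline prints the sum-based rule, the SAP follows its source and the oddity belongs to the published method. This stands. A reader might infer from the table that the SAP has made a scoring error and that one-item responders are simply scored 67 points too low. The documents do not support that, because the guideline cannot be seen here. They show that the printed rule differs from one-item scaling by up to 66.7 points, and that it sits badly with the Q5c row.

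It can also be said that the item coding is inferred. That is true, but no other coding fits the divisors, the zero-sum branch and the separate treatment of a zero Q5c together so readily.

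A third objection is that the consequences are small. Only one of nine KHQ domains is involved. Protocol 13.1.3.3.1 plans only summary statistics for the KHQ. SAP 8.1.8 adds tests and intervals but no covariance or repeated-measures model, and the KHQ is not among the pairings in SAP Figure 8-1. All of this stands and sets the priority of the point. A reader might also infer that the treatment comparison is biased in one direction. Nothing in the documents supports that: the same rule applies to both blinded groups, and for a patient whose applicable item stays the same, change is shrunk or lost but never reversed in sign.

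Finally, counting answered items does not cure every problem. If (0,4) becomes (1,4), the printed rule gives 33.3 to 50 and the items-answered rule gives 100 to 50. The domain's item content has changed under either rule.

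**Conclusion.** The point holds as an internal inconsistency in Table 6-1 that should be resolved. Assuming not applicable is coded 0 and answers run 1 to 4, the one-item formula has no effect as printed. A one-item responder cannot score above 33.3, and six of 25 response pairs differ from items-answered scoring, by 33.3 to 66.7 points. Within-patient change for one-item responders is at most half of its one-item value, and false change can appear when applicability shifts between visits.

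The documents do not give the number of patients with exactly one applicable item, so the effect on group results cannot be sized beyond the per-patient figures. The primary endpoint, BCI or PIP1, is unaffected. Whether the printed row departs from its source or reproduces it remains open until the guideline is checked.

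**What to change.** Before unblinding, check the Personal relationships row against the cited guideline, and state in SAP 6.1.1.4 how items are coded and how one not-applicable item is scored.

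- If the guideline does not print the sum-based rule, choose the branch by items answered. Both at least 1: (Q5a + Q5b − 2)/6 × 100. Exactly one at least 1: (that score − 1)/3 × 100. Neither: missing.
- If the guideline prints the sum-based rule, keep it for comparability with the published method, and add the items-answered score as a prespecified sensitivity analysis of the SAP 8.1.8 analyses for this domain.

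In either case, report by group and visit how many patients had two, one or no applicable items, since a change in applicability alters what the domain measures under both rules.

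The first option costs three lines in Table 6-1, and the second costs one extra set of outputs for one domain. The downside is that items-answered scores for one-item responders may differ from the published method. If unblinding has already taken place, SAP section 10 requires the addition to be recorded separately from the analyses planned in advance.

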6.1.1.5 Bladder Diary Records

The times of urination, times of urinary incontinence, whether urinary urgency is present, and voided volume for each urination will be evaluated using Bladder Diary records.

The average number of daytime urinations is defined as follows. Nocturnal urination is defined as urination after bedtime on the day and before wake-up on the next day.

Average number of daytime urinations = average number of micturitions per 24 hours – average number of nocturnal urinations

6.1.2 Safety Endpoints

6.1.2.1 Adverse Events and Adverse Reactions

An adverse event is any untoward medical occurrence in a patient participating in the study. Adverse events for which a causal relationship with the investigational product is assessed as “reasonably possible” are considered to be adverse reactions.

6.1.3 Endpoints for Treatment Compliance

6.1.3.1 Compliance Rate

The definition of compliance rate in the observation and treatment periods is shown below.

[1] Observation period

Compliance rate during the observation period (%) = (number of doses with no dose modification/interruption during the observation period) / (prescribed number of doses from the first dose of investigational product during the observation period to the last dose of investigational product during the observation period) × 100

[2] Treatment period

Compliance rate during the treatment period (%) = (number of doses with no dose modification/interruption during the treatment period) / (prescribed number of doses from the first dose of investigational product during the treatment period to the last dose of investigational product during the treatment period) × 100

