Checking of drug compliance			X	X		X		X		X		X
Physical examination	X		X	X		X		X		X	X	X
Blood pressure, pulse rate, and body temperature	X ⁹⁾		X	X		X		X		X	X	X
12-lead electrocardiography	X ⁹⁾		X							X	X	X
Laboratory tests ³⁾	X ⁹⁾		X	X		X		X		X	X	X
Pregnancy tests ⁴⁾	X											
Bladder diary records: Supplied	X			X		X		X				
Filled in												
Collected			X			X		X		X		X
Checked			X			X		X		X		X
Symptom score (IPSS, OABSS) evaluation	X		X			X		X		X		X
King's health questionnaire evaluation			X							X		X
Pressure Flow Study (PFS) ¹⁰⁾			X							X		X
Uroflowmetry			X ¹¹⁾			X ¹¹⁾		X ¹¹⁾		X ¹¹⁾		X ¹¹⁾
Post void residual measured by ultrasound	X ⁹⁾		X ¹¹⁾			X ¹¹⁾		X ¹¹⁾		X ¹¹⁾		X ¹¹⁾
Prostate gland volume measurement	X ⁹⁾											
Checking concomitant drugs/concomitant therapy ¹²⁾												X
Checking adverse events ¹²⁾												X

- 1) Obtaining informed consent: Obtained within the period of 28 days before registration in the observation period.
- 2) Assigning of patient identification codes: Assigned to patients providing informed consent.
- 3) Laboratory tests: Hematology tests, biochemistry tests, endocrinological tests and urinalysis will be performed. However, the urinalysis test urine sediment will only be performed at registration in the observation period and at registration in the treatment period.
- 4) Pregnancy tests: Required for female patients with childbearing potential. However, a pregnancy test will not be required for patients more than 1 year after menopause or patients in whom the possibility of pregnancy is medically ruled out. At tests before registration in the observation period, pregnancy tests (serum or urine) must be negative. The time window for performing the test is the period of 7 days before registration in the observation period.
- 5) Time window for registration in the treatment period: All observation and examination items at registration in the treatment period will be performed by registration in the treatment period, 2 to 4 weeks after registration in the observation period.
- 6) Time window for visits in the treatment period: Visits at weeks 2, 4, and 8 of the treatment periods will be allowed to be within the range of the standard date ± 3 days. The visit at week 12 will be allowed to be within the range of the standard date -3 days to the standard date $+7$ days.

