7.1.1.2 Treatment period

In the treatment period, under double-blind conditions, the investigational drug (TAC-302 or placebo) will be administered orally twice daily after breakfast and dinner for 12 weeks. The number of investigational drug capsules per dose is shown in [Table 7.1.1.2-1](#).

**Table 7.1.1.2-1 Number of Investigational Drug Capsules Per Dose
(Treatment Period)**

Group	Number of capsules per dose
TAC-302	TAC-302 100 mg × 2 capsules
Placebo	Placebo × 2 capsules

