3.2 Analysis Sets

The analysis sets and their definitions are shown in Table 3-2. If there are patients for whom attribution to analysis sets is problematic based on factors other than the criteria shown below, handling of such patients will be determined by discussion between the sponsor and medical expert, etc. The primary efficacy analysis set will be PPS, and the primary safety analysis set will be all treated patients in the treatment period.

Table 3-2 Definition of Analysis Sets

Analysis Sets	Definition
Screening Patients	All patients who gave informed consent
All enrolled patients in the observation period	The set of all patients who were enrolled in the observation period
All enrolled patients in the treatment period	The set of all patients who were enrolled in the treatment period
All treated patients in the observation period	The set of patients enrolled in the observation period who took the investigational drug at least once
All treated patients in the treatment period	The set of patients enrolled in the treatment period who took the investigational drug at least once
Full Analysis Set(FAS)	The set of patients enrolled in the treatment period who took the investigational drug for the treatment period at least once and who had at least 1 efficacy endpoint measurement before the start of the treatment period and in the treatment period
Per Protocol Set(PPS)	The set of patients in the FAS, excluding patients who met any of the following criteria: (1) Being discovered to have a violation of the inclusion criteria (2) Being discovered to meet any of the exclusion criteria (criteria affecting efficacy evaluation) (3) A compliance rate for the treatment period of < 80% (4) Being administered prohibited concomitant drugs or prohibited concomitant therapy considered likely to influence efficacy evaluation (5) No evaluation of the primary endpoint at Week 12 of the treatment period

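### The SAP compliance rate stops counting at the patient's own last dose, so the 80% rule for the per protocol set cannot see a late stop in dosing

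*SAP*

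**What the plan says.** SAP section 6.1.3.1, item [2], gives the only formula for treatment-period compliance in the two documents. The numerator is the number of doses without modification or interruption. The denominator is the number prescribed "from the first dose of investigational product during the treatment period to the last dose of investigational product during the treatment period". Neither Week 12 nor a scheduled end of dosing is mentioned.

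SAP section 3.2 states: "The primary efficacy analysis set will be PPS". Criterion (3) in Table 3-2 removes patients with "A compliance rate for the treatment period of < 80"%, and criterion (5) removes those with "No evaluation of the primary endpoint at Week 12 of the treatment period". Protocol section 13.1.2.1 carries the same two criteria and gives no formula of its own.

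The schedule is in Protocol section 7.1.1.2: "the investigational drug (TAC-302 or placebo) will be administered orally twice daily after breakfast and dinner for 12 weeks". Protocol Table 5-2 places compliance checks at Weeks 2, 4, 8 and 12. Under note 6 to that table the Week 8 visit may fall 3 days either side of its standard date, and the Week 12 visit from 3 days before to 7 days after. The PFS that supplies the primary endpoint is done at Weeks 0 and 12.

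**The concern.** A compliance threshold for a per protocol set is normally there to remove patients who did not take enough of the assigned treatment for the endpoint to reflect it. Here, doses prescribed but not taken after the last dose appear in neither numerator nor denominator. The rule sees gaps between doses but not a gap at the end, and the end is the part closest to the Week 12 PFS.

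Most early stops should be caught in other ways: at a visit check, by discontinuation, or by criterion (5) if the Week 12 PFS is missing. What remains is mainly the patient who stops after the Week 8 check, is not formally discontinued, and still attends for the Week 12 PFS. No PPS criterion removes that patient.

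At stake is consistent membership of the primary efficacy set. One stated rule keeps a patient who has been off drug for more than two weeks at the PFS and excludes another who took the same number of doses and was still dosing.

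**Working it through.** The documents give no worked compliance figure to reproduce, so the check applies the SAP formula to the protocol schedule.

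**Inputs**
- Two doses a day for 12 weeks (Protocol 7.1.1.2): 84 × 2 = 168 doses.
- Threshold 80% (SAP Table 3-2): 0.80 × 168 = 134.4, so 134 doses or fewer fail.
- Week 8 check on day 56, window day 53 to 59. Week 12 PFS on day 84, window day 81 to 91 (Protocol Table 5-2, note 6).
- Assumptions: day 84 is the standard Week 12 date, both doses of each day count, and no dose is missed before the stop.

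**Formulas, for a stop after day d**
- SAP rate = 2d / 2d.
- Share of schedule = 2d / 168.
- Days off drug at a day-84 PFS = 84 − d.

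| Stop after day | SAP rate | Share of schedule | Days off drug |
|---|---|---|---|
| 53 | 106/106 = 100% | 106/168 = 63.1% | 31 |
| 56 | 112/112 = 100% | 112/168 = 66.7% | 28 |
| 59 | 118/118 = 100% | 118/168 = 70.2% | 25 |
| 67 | 134/134 = 100% | 134/168 = 79.8% | 17 |
| 68 | 136/136 = 100% | 136/168 = 81.0% | 16 |

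Day 67 is the last whole-day stop that falls below 80% of the schedule. The stops whose classification depends on the denominator therefore run from the Week 8 check (day 53 to 59) to day 67.

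**Same exposure, opposite result.** With 134 doses, scattered misses and a last dose on day 84, the SAP rate is 134/168 = 79.8% and the patient is excluded. With 134 doses taken without a miss and then a stop, it is 134/134 = 100% and the patient is kept.

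**Sensitivity of the day-67 boundary**
- PFS on day 81 (162 doses, 80% = 129.6): day 64 gives 128/162 = 79.0%; day 65 gives 130/162 = 80.2%.
- PFS on day 91 with dosing prescribed to that visit (182 doses, 80% = 145.6; the documents do not say whether it is): day 72 gives 144/182 = 79.1%, 19 days off drug; day 73 gives 146/182 = 80.2%.
- Doses of the PFS day not counted (168 − 2 = 166): day 66 gives 132/166 = 79.5%; day 67 gives 134/166 = 80.7%.
- 10% of doses missed before the stop: the SAP rate is 90% whatever the stop day. Against 168, stops up to day 74.5 fail (149 × 0.9 / 168 = 79.8%).

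**Check of a fixed denominator of 168 as a remedy.** If dosing is prescribed to a day-91 visit, full adherence would score 182/168 = 108%, and 135 doses taken would score 135/168 = 80.4% (kept) instead of 135/182 = 74.2% (excluded). The denominator has to be patient-specific.

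**Limit of any rate.** If dosing is prescribed only to day 84 and the PFS is on day 91, a stop at day 68 gives 136/168 = 81.0% and is kept, with 91 − 68 = 23 days off drug. The off-drug interval has to be listed as well.

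**The case against.** The arithmetic is not in dispute. The case on the other side concerns consequence and reading.

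- **Little depends on it.** The primary analysis is a by-group summary (SAP 7.1), repeated in the full analysis set (FAS) without the compliance rule (7.2), and the between-group analyses run in both sets (7.3). This stands and is why the weight is minor.
- **The chain is long.** An adherent patient must stop in a window of roughly 8 to 14 days (67 − 59 to 67 − 53), avoid discontinuation and still return for an invasive test. This also stands. Nothing in the documents shows that such a patient exists.
- **The stop would be seen.** Leftover drug is retrieved and compliance checked at Week 12, using diaries, empty sheets and interview (Protocol 5.1.6). True, but the formula does not use what is found.
- **Patient-level review can intervene.** Set membership enters as a supplied flag (SAP Table 3-1), blind review precedes unblinding, and for problem cases "handling of such patients will be determined by discussion between the sponsor and medical expert, etc". Further detail may be in the efficacy data handling table and the report analysis plan, neither of which was available. These routes are discretionary or unseen. The discussion route in SAP 3.2 is for problems outside the listed criteria, whereas this patient passes a listed criterion at 100%.
- **The last dose might mean the last prescribed dose.** Then the gap disappears. The text does not say so, and beside a first dose that can only be the actual one, the natural reading is the actual last dose. The wording would still need correcting.
- **Adherence while on treatment is a legitimate measure.** It is, and it can stay as a descriptive summary. That does not make it a suitable sole measure for deciding who belongs in a per protocol set.

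**Conclusion.** The concern holds. As written, a stop in dosing cannot lower the compliance rate, so PPS criterion (3) cannot detect one. With a day-84 PFS and no earlier misses, the affected stops run from the Week 8 check (day 53 to 59) to day 67. The end point moves to day 64 with a day-81 PFS, and to day 72 with a day-91 PFS if dosing is prescribed to that visit. Later stops stay above 80% with either denominator. Criterion (3) can still exclude such a patient for doses missed before the stop.

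The conclusion rests on reading the last dose as the patient's actual last dose. Neither the number of patients affected nor any dilution of the treatment effect can be derived from the documents, and none is claimed. The rule is wrong as written but of minor weight. It is worth correcting because it decides membership of the primary efficacy set and the correction is cheap.

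**What to change.** Before unblinding:

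1. Keep the existing rate for the descriptive compliance summary in SAP 8.2.2.
2. For PPS criterion (3) only, add a separately labelled rate to SAP 6.1.3.1. Its denominator is the number of doses prescribed from the first treatment-period dose to the earlier of the Week 12 PFS and the end of that patient's prescribed dosing, whether or not they were taken. That is 168 for 84 days, 162 for a day-81 PFS, and more than 168 only if dosing was prescribed to a later visit. Count numerator doses over the same interval, with the existing definition of a counted dose.
3. Cite this rate in criterion (3) of SAP Table 3-2.
4. List days from last dose to the Week 12 PFS for each PPS patient.

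The cost is one definition, one cross-reference and one listing column. No new data are needed: compliance is already checked at each visit, and total dose and duration are already summarised (SAP 8.2.1). The downside is that the PPS may lose a few patients and two compliance rates must be kept apart in the tables.
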